4/18/2020	Schema and throughout	Changed the Interim Response Assessment to take place during days 39-42 (instead of day 36 ± 5 days) and for cycle 2 to start within 2 weeks (instead of 3 weeks) of the end of cycle one treatment
4/18/2020	4.1.5	Added highly effective methods of contraception
4/18/2020	8.1.1.1	Updated the language for second primary malignancies and removed pregnancy and breastfeeding from the warning and precautions section
4/18/2020	8.3; 8.4; 8.5	Added the definition of AESI and included AESIs in the reporting requirements to go along with SAEs
12/28/2020	Cover Page	Remove University Hospitals; Update Cleveland Clinic sub-investigators and study coordinator
12/28/2020	5.0	Registration contact information changed from [name] to the Study Coordinator provided on page 2
12/28/2020	8.5.1	SAE/AESI Reporting Requirements: study coordinator added to list of people included in notification
12/28/2020	6.1.3; 9.2	Adding biosimilar use of Rituximab is permitted for this study per treating investigator discretion
12/28/2020	10.3	Change Cleveland Clinic Biorepository shipping title and ATTN to [name]

Protocol Date	Section	Change
12/28/2020	6.5; 11.1.2; 11.2	Allowing virtual visits for long-term follow up visits
7/2/2021	Cover page	Updated study staff
7/2/2021	Abbreviations	Removed unused abbreviations
7/2/2021	Table of contents	Added missing section numbers
7/2/2021	throughout	Corrected typos
7/2/2021	Schema; 11.1.1; 11.2	Added required PT/INR at screening to align with inclusion criteria
7/2/2021	9.1	Corrected storage temperature of acalabrutinib
7/2/2021	11.1.1	Removed requirement to receive approval for missing tissue samples prior to enrollment
7/2/2021	13.1	Replaced references to Forte EDC with the new name Adverra EDC

Figure 1: STUDY SCHEMA

PROTOCOL SUMMARY

Protocol Number/Title	CASE 3419/ Phase II Study of Rituximab and Acalabrutinib in Newly Diagnosed B Cell Post Transplant Lymphoproliferative Disorder (PTLD)
Study Phase	Phase II
Brief Background/Rationale	
Post-transplant lymphoproliferative disorders (PTLD) are rare pathologically and clinically heterogeneous diseases that occur in both solid organ and bone marrow transplant (BMT) patients. The frequency of PTLD in solid organ transplant (SOT) varies from 1-20% with highest incidence seen among heart, lung, intestinal and multi organ transplantation ¹⁻⁵
 
Currently there is no approved therapy for PTLD. Single agent rituximab is commonly used and the overall response rate (ORR) has ranged from 37% to 69% ⁶⁻¹¹. In a subset of patients' inadequate response necessitates addition of chemotherapy to improve response rate and outcomes. The morbidity and mortality with combination chemotherapy is reported to be high in this population ⁸. In one analysis 52% patients treated with chemotherapy required hospital admission for complications and treatment related mortality was 26% ⁸. Due to these reasons treatment with novel targeted agents needs to be explored to improve outcomes and to minimize toxicity.
 
Acalabrutinib is a well-tolerated Bruton's Tyrosine Kinase Inhibitor (BTK). BTK plays an important role in B cell development and function thus its inhibition is a treatment strategy in B cell lymphomas. Acalabrutinib has been approved in the treatment of R/R mantle cell lymphoma (MCL) and is being studied in other B cell malignancies ¹²⁻¹⁵.

Primary Objective	To determine the overall response rate to combination treatment with rituximab and acalabrutinib in patients with PTLD. To be measured 8 weeks after treatment completion.
Secondary Objective(s)	
To determine the following in patients with PTLD treated with combination rituximab and acalabrutinib.
 
 • Complete response rate (CRR) • Partial response rate (PRR) • Duration of response (DOR) • Progression free survival (PFS) • Overall survival (OS) • Time to treatment failure (TTF) • Safety of rituximab and acalabrutinib
Sample Size	62 patients
Disease sites/Conditions	Post-transplant lymphoproliferative disorder

Interventions	
• Rituximab weekly x 4 weeks PLUS acalabrutinib 100mg BID x 4 weeks (28 day cycle)• Response assessment with CT scans on days 39-42 after end of cycle 1 treatment.• If complete response, then proceed with one additional 28 day cycle.• If partial response, then proceed with 3 additional 28 day cycles.• If stable disease or progression of disease, then go off study treatment and proceed onto LTFU.
---------------	--

ABBREVIATIONS

AE	adverse event
AESI	adverse events of special interest
ALT	alanine aminotransferase
ANC	absolute neutrophil count
AST	aspartate aminotransferase
BCR	B cell receptor
BID	twice per day (dosing)
BOR	best overall response
BR	Bendamustine and Rituximab
BTK	Bruton tyrosine kinase
BMT	Bone marrow transplant
BUN	blood urea nitrogen
CBC	complete blood count
CCCC	Case Comprehensive Cancer Center
CCF	Cleveland Clinic Foundation
CFR	Code of Federal Regulations
ClIs	confidence intervals
CLL	chronic lymphocytic leukemia
CR	complete response (remission)
CRF	case report form
CT	computed tomography
CTCAE	Common Terminology Criteria For Adverse Events
CYP	cytochrome p450
DOR	duration of response
DSTC	Data Safety and Toxicity Committee
ECG	electrocardiogram
ECOG	Eastern Cooperative Oncology Group
FDA	Food and Drug Administration
GCP	Good Clinical Practice
HBV	hepatitis B virus
HCV	hepatitis C virus
HIV	human immunodeficiency virus
ICF	informed consent form
IB	Investigator's brochure
IEC	independent ethics committee
Ig	immunoglobulin
IRB	institutional review board

IV	intravenous or intravenously
LDH	lactate dehydrogenase
MedDRA	Medical Dictionary for Regulatory Activities
MCL	mantle cell lymphoma
NE	nonevaluable
NHL	Non-Hodgkin lymphoma
ORR	overall response rate
OS	overall survival
PFS	progression-free survival
PLL	prolymphocytic leukemia
PR	partial response (remission)
PRL	partial response with lymphocytosis
PRMC	Protocol Review and Monitoring Committee
PTLD	post-transplant lymphoproliferative disorders
R/R	relapsed/refractory
SAE	serious adverse event
SD	stable disease or standard deviation
SOC	Standard of Care
SOT	solid organ transplant
SUSAR	suspected unexpected serious adverse reaction
TTF	time to treatment failure
ULN	upper limit of normal

TABLE OF CONTENTS

1.0 Introduction

1.1 Background of PTLD

Post-transplant lymphoproliferative disorders (PTLD) are rare pathologically and clinically heterogeneous diseases that occur in both solid organ and bone marrow transplant (BMT) patients. The main determinant risk factors in the development of PTLD are the degree and duration of the immunosuppression. Suppression of the normal T cell function by the immunosuppressants enables the proliferation of EBV infected B cells leading to the development of PTLD.

The frequency of PTLD in solid organ transplant (SOT) varies from 1-20% with highest incidence seen among heart, lung, intestinal and multi organ transplantation ¹⁻⁵. The higher incidence of PTLD among these SOTs has been attributed to higher degree and longer duration of immunosuppression. The incidence is much less (1-5%) in SOT that requires lower immunosuppression like liver and renal transplants ^{4,5}. The incidence in BMT patients is low approximately 0.5-1% with T cell depletion being a risk factor ¹⁶⁻¹⁸.

The highest incidence of PLTD is in 1-2 years following the transplant. Early PTLD are mostly EBV positive, while the late PTLDs have shown to be EBV negative ^{19,20}. According to the 2016 WHO classification, PTLD is classified into 6 categories: plasmacytic hyperplasia PTLD, infectious mononucleosis PTLD, florid follicular hyperplasia PTLD, polymorphic PTLD, monomorphic PTLD and classical Hodgkin lymphoma PTLD ²¹. Due to paucity of data and rarity of the disease there is no well-established standard of care for PTLD.

Currently, PTLD is treated with either single agent rituximab or with rituximab containing chemotherapy. The overall response rate (ORR) to single-agent rituximab has ranged from 37% to 69% ⁶⁻¹¹. The first prospective phase II study by Choquet et al evaluated single-agent rituximab in 43 SOT-related PTLD recipients who failed tapering of immunosuppression ⁷. They demonstrated an ORR of 34%, event free survival (EFS) of 72%, and overall survival (OS) of 67% at 1 year. Complete response (CR) rate in this trial after 4 doses of rituximab was 28%. Rituximab was well tolerated with only 2 grade 3 or 4 events related to rituximab – hypertension and purpura with myalgia. Neutropenia was reported in two patients ⁷. Another prospective study evaluated the efficacy of extended use of rituximab in 38 patients with PTLD ¹¹. After the first course of rituximab, 34% had a CR, which was further augmented to 61% when partial responders were given 4 additional doses. One episode of grade 4 neutropenia was the only serious adverse event observed. Elstrom et al retrospectively reviewed 35 patients with PTLD treated with rituximab and showed an ORR of 68% and median OS of 31 months with rituximab ⁸.

Currently there is no approved therapy for PTLD. Although single agent rituximab is commonly used to treat B cell PTLD, the overall response rate is around 60% with approximately 30% of the subjects attaining a complete response. In a subset of patients' inadequate response necessitates addition of chemotherapy to improve response rate and outcomes. The morbidity and mortality with combination chemotherapy is reported to be high in this population ⁸. In one analysis 52% patients treated with chemotherapy required hospital admission for complications and treatment related mortality was 26% ⁸. Due to these reasons treatment with novel targeted agents needs to be explored to improve outcomes and to minimize toxicity.

1.2 Name and Description of Acalabrutinib

1.2.1 Preclinical Data

Acalabrutinib is a potent inhibitor of BTK in vitro and in vivo. Pharmacology models have been used to define kinase selectivity of acalabrutinib in comparison to other BTK inhibitors, and to investigate functional effects of on-target and off-target activities. Acalabrutinib shows improved selectivity for BTK compared with ibrutinib ²². Functional inhibition of non-target cells (eg, T cells, NK cells, platelets) was not observed for acalabrutinib at clinically relevant concentrations. Acalabrutinib is orally bioavailable in humans and is suitable for formulating in capsules. Acalabrutinib is approved in the US for the treatment of adult patients with mantle cell lymphoma (MCL) who have received at least 1 prior therapy. It is also being evaluated for the treatment of patients with other B-cell malignancies.

Please refer to the Investigator's Brochure (IB) for detailed preclinical data.

1.2.2 Clinical Efficacy Data

There have been several studies and are several ongoing studies that have evaluated the efficacy of acalabrutinib in B cell malignancies and even solid tumors. Acalabrutinib is approved for R/R mantle cell lymphoma and undergoing a phase III studies for use in chronic lymphocytic leukemia (CLL). A summary of results from studies evaluating acalabrutinib is below however, please see the Investigator Brochure for full details.

In a phase II study (ACE-LY-004) using single agent acalabrutinib to treat R/R MCL the ORR in 124 patients was 80.6% with 39.5% achieving a CR ²³. More than half of patients (56.6%) continued on treatment at a median follow up of 15 months. The median duration of response, PFS and OS were not reached, but the 1-year PFS and OS were 67% and 87% respectively ²³. Most adverse events (AE) were grade 1-2, with only a small proportion of the patients experiencing grade ≥ 3 AE, which included neutropenia (10%), anemia (9%) and pneumonia (5%). Only 1 patient had grade 3 bleeding, while no atrial fibrillation was noted. Other notable AEs include grade 2 pneumocystis jirovecii pneumonia (PJP) and cytomegalovirus (CMV) reactivation in 1 patient ²³. Acalabrutinib is being evaluated with Bendamustine and Rituximab (BR) for the treatment of MCL in a Phase 1b, multicenter, open label study (ACE-LY-106) ²⁴. The study includes two cohorts – treatment-naïve and R/R patients. The ORR was 94.4% (n=18) in the treatment-naïve cohort and 80.0% (n=20) in the R/R cohort. The phase III randomized placebo-controlled study evaluating BR vs BR + acalabrutinib in newly diagnosed MCL is currently accruing (clinicaltrials.gov #NCT02972840).

ACE-CL-001 is a phase I/II study of single agent acalabrutinib in 134 patients with R/R CLL, 99 patients with treatment-naïve CLL, 33 patients with CLL that were ibrutinib-intolerant, and 29 patients with Richter's syndrome or prolymphocytic leukemia transformation (PLL) ²⁵. Acalabrutinib 100 mg twice-daily dose demonstrated 99% BTK occupancy. In the R/R CLL cohort, ORR (including PR and PRL) was 96.9% with most responses being PR (86.8%) at a median follow up of 19.8 months. The rate of PFS at 12 months was 95.4% ^{13,14}. In the treatment-naïve and ibrutinib intolerant cohorts the ORRs were 99% and 80.6%, respectively. In the Richter's syndrome or PLL group the ORR was 37%. Ongoing studies are evaluating acalabrutinib in combination with chemotherapy in various subtypes of B cell malignancies.

1.2.3 Clinical Pharmacokinetics

Acalabrutinib is an imidazopyrazine analogue with a molecular weight of 465.5 g/mol. The compound has 1 stereogenic center and acalabrutinib is the S-enantiomer. See the IB for further details regarding pharmacokinetics. In brief, Acalabrutinib is absorbed rapidly in non-clinical

species. It is almost completely metabolized by multiple CYP and non CYP metabolic pathways with CYP3A-mediated oxidation being the major route of metabolism. The half-life of the active metabolite (ACP-5862) is 6.9 hours. Acalabrutinib is excreted mostly in the feces (84%) and a small amount in the urine (12%).

1.3 Name and Description of Rituximab

Rituximab has been approved for the use in Non-Hodgkin's Lymphoma (NHL), Chronic Lymphocytic Leukemia (CLL), Rheumatoid Arthritis, Granulomatosis with Polyangiitis and Microscopic Polyangiitis, and Pemphigus Vulgaris²⁶. While not approved for PTLD, it has become the mainstay of treatment (see Section 1.1 for further details)

1.3.1 Preclinical Data

Rituximab is a genetically engineered, chimeric murine/human monoclonal antibody directed against the CD20 antigen found on the surface of normal and malignant pre-B and mature B cells. The antibody is an IgG1 κ immunoglobulin containing murine light-and heavy-chain variable region sequences and human constant region sequences. Rituximab is composed of two heavy chains of 451 amino acids and two light chains of 213 amino acids (based on cDNA analysis) and has an approximate molecular mass of 145 kD. The Fab domain of rituximab binds to the CD20 antigen on B-lymphocytes with a binding affinity of ~8.0nM. The Fc domain recruits immune effector functions. Upon binding to CD20, rituximab mediates B-cell lysis. Possible mechanisms of cell lysis include complement dependent cytotoxicity (CDC) and antibody dependent cell mediated cytotoxicity (ADCC). The biological effect is manifested by B-cell depletion in peripheral blood, lymph nodes, and bone marrow²⁶.

1.3.2 Clinical Efficacy Data

See section 1.1 for discussion of rituximab use in patients with PTLD.

1.3.3 Clinical Pharmacokinetics

Per the rituximab package insert, pharmacokinetics were characterized in 203 NHL patients receiving 375 mg/m² rituximab weekly by intravenous infusion for 4 doses. Rituximab was detectable in the serum of patients 3 to 6 months after completion of treatment. The pharmacokinetic profile of rituximab when administered as 6 infusions of 375 mg/m² in combination with 6 cycles of CHOP chemotherapy was similar to that seen with rituximab alone. Based on a population pharmacokinetic analysis of data from 298 NHL patients who received rituximab once weekly or once every three weeks, the estimated median terminal elimination half-life was 22 days (range, 6.1 to 52 days). Patients with higher CD19-positive cell counts or larger measurable tumor lesions at pretreatment had a higher clearance. However, dose adjustment for pretreatment CD19 count or size of tumor lesion is not necessary. Age and gender had no effect on the pharmacokinetics of rituximab.

Pharmacokinetics were characterized in 21 patients with CLL receiving rituximab according to the recommended dose and schedule. The estimated median terminal half-life of rituximab was 32 days (range, 14 to 62 days)²⁶.

1.4 Rationale

As stated in the Section 1.1, there is currently no approved therapy for PTLD. Single agent rituximab and combination chemotherapy (R-CHOP) are the treatments used in clinical practice. Single agent rituximab yields a response rate of around 60% and combination chemotherapy is associated with significant morbidity and mortality⁸. As there are no approved treatment for newly diagnosed or relapsed PTLD, it's an area of unmet need. Due to these

reasons treatment with novel targeted agents needs to be explored to improve outcomes and to minimize toxicity.

Bruton's tyrosine kinase (BTK) is a non-receptor enzyme in the Tec kinase that plays an important role in B-cell development and function. It is in the B-cell receptor (BCR) signaling pathway and leads to the activation of nuclear factor kB and thus cell migration, proliferation and survival. Abnormal signaling of the BCR pathway is important in the pathogenesis of B-cell malignancies. Thus, inhibition of the BTK has been implicated in the treatment of B-cell malignancies ^{12,15}

Acalabrutinib is a highly selective, irreversible second-generation Bruton's tyrosine kinase (BTK) inhibitor that is approved for the treatment of mantle cell lymphoma (MCL), a B cell malignancy. It is also active in CLL and studies are ongoing evaluating its efficacy in other B cell lymphomas. This drug is rapidly absorbed and eliminated reaching the mean peak plasma level between 0.6 to 1.1 hours with a mean half-life of 1 hour in CLL patients ¹³. This short half-life compared to 4-6 hours for ibrutinib ²⁷ could be partially responsible for its better safety profile. Unlike ibrutinib, published data suggests lack of inhibition of epidermal growth factor receptor (EGFR), interleukin-2 inducible T cell kinase (ITK) and tyrosine kinase expressed in hepatocellular carcinoma (TEC) by acalabrutinib ¹³. An aggregate safety analysis of acalabrutinib monotherapy was conducted and included data from 7 studies. This pooled data included 614 acalabrutinib-exposed subjects with a median exposure of 21.9 months. The most frequently reported Grade ≥ 3 AEs were neutropenia (10.4%), anemia (7.5%), pneumonia (6.5%), thrombocytopenia (3.7%), and hypertension (3.1%). Evidence of clinical activity with improved toxicity profile has led to clinical studies with this agent in B cell malignancies.

Ongoing studies are evaluating combination of acalabrutinib in various subtypes of B cell malignancies. Some of which include acalabrutinib with bendamustine and rituximab (BR) in RR MCL (NCT02717624), and in combination with R-CHOP in DLBCL (ACCEPT trial). An ongoing trial in United Kingdom is evaluating the outcome of ibrutinib with R-CHOP in PTLD patients (<https://bloodwise.org.uk/research/clinical-trials/ptld-ibrutinib-i-and-rituximab-r-and-ir-chop>). Based on emerging data of clinical efficacy of acalabrutinib in B cell malignancies and an unmet need for novel therapies in PTLD, we propose a phase II study of rituximab and acalabrutinib in newly diagnosed B cell PTLD.

2.0 Objectives

2.1 Primary Objective

To determine the overall response rate to combination treatment with rituximab and acalabrutinib in patients with newly diagnosed B-cell PTLD.

2.2 Secondary Objectives

To determine the following in patients with PTLD treated with combination rituximab and acalabrutinib.

- Complete response rate (CRR)
- Partial response rate (PRR)
- Duration of response (DOR)
- Progression free survival (PFS)
- Overall survival (OS)
- Time to treatment failure (TTF)
- Safety of rituximab and acalabrutinib

3.0 Study Design

3.1 Study design

This is a non-randomized phase II study of acalabrutinib plus rituximab in newly diagnosed B-cell PTLD in both SOT and BMT patients. All subjects who meet the eligibility criteria described below will be enrolled to participate in the study.

Refer to Section 11 for a comprehensive list of study assessments and their timing. The study schema is provided in Figure 1 at the beginning of this document

3.2 Number of Subjects

We plan to enroll 62 patients.

3.3 Replacement of Subjects

If a subjects signs consent and meets eligibility criteria, but withdraws from the study prior to receiving the study treatment, the subject will be replaced. No subject will be replaced after receiving study treatment.

3.4 Expected Duration of Treatment and Subject Participation

Duration of treatment will depend on patients' response to therapy. Initial treatment (cycle 1) for all patients, will be 28 days in length. Between days 39-42 after the end of cycle 1 treatment, patients will undergo CT scan for response assessment. Patients with a complete response will receive one additional 28 day cycle of therapy. Patients with a partial response will receive 3 additional 28 day cycles of therapy. Patients with stable disease or progressive disease will come off study treatment and go directly on to long-term follow-up. Patients will receive a minimum of 1 cycle of therapy and a max of 4 cycles depending on their response. Cycle 2 should start within 2 weeks after the end of cycle 1 treatment.

Table 1: Total Duration of Treatment Based on Disease Response

Response to Cycle 1	Duration of Treatment
Complete Response	56 days
Partial Response	112 days
Stable or Progressive Disease	28 days

4.0 Subject Selection

Each of the criteria in the sections that follow must be met in order for a subject to be considered eligible for this study. Use the eligibility criteria to confirm a subject's eligibility.

4.1 Inclusion Criteria

Subjects must meet all of the following inclusion criteria to be eligible for enrollment:

- 4.1.1 Subjects must have a biopsy confirmed newly diagnosed CD20 positive B cell PTLD. The histological diagnosis may include:

- Plasmacytic hyperplasia PTLD
- Infectious mononucleosis PTLD
- Florid follicular hyperplasia PTLD
- Polymorphic PTLD
- Monomorphic PTLD (B- cell types)
- Classical Hodgkin lymphoma PTLD

4.1.2 Patients \geq 18 years of age.

4.1.3 Eastern Cooperative Oncology Group (ECOG) performance status of 0-2. ECOG 3 will be permitted if the decline in performance status is due to lymphoma. [See Appendix 1]

4.1.4 Subjects must have adequate hematologic, hepatic, and renal function as defined below:

- Hemoglobin \geq 8 gm/dL
- Absolute neutrophil count \geq 1000/mcL (unless documented bone marrow involvement with lymphoma)
- Platelet count \geq 50000/mcL (unless there is documented bone marrow involvement with lymphoma)
- Prothrombin time/INR or aPTT (in the absence of Lupus anticoagulant) $<$ 2x ULN.
- Total bilirubin \leq 1.5X upper limit of normal (ULN)
- Creatinine \leq 2.5X upper limit of normal (ULN) or creatinine clearance \geq 40 ml/min using the Cockcroft-Gault equation (Appendix 4)
- ALT/AST $<$ 2.5 X or \leq 5X ULN for patients with documented hepatic involvement with lymphoma

4.1.5 Women of childbearing potential and men must agree to use highly effective methods of contraception during treatment and for 12 months after last dose of study treatment. Such methods include:

- Combined (estrogen and progestogen containing) hormonal contraception associated with inhibition of ovulation, which may be oral, intravaginal, or transdermal
- Progestogen-only hormonal contraception associated with inhibition of ovulation, which may be oral, injectable, or implantable
- Intrauterine device (IUD) or intrauterine hormone-releasing system (IUS)
- Bilateral tubal occlusion
- Vasectomy of a female subject's male partner (with medical assessment and confirmation of vasectomy surgical success)
- Sexual abstinence (only if refraining from heterosexual intercourse during the entire period of risk associated with the study treatments)

Women who have undergone surgical sterilization or who have been postmenopausal for at least 2 years are not considered to be of childbearing potential.

4.1.6 Subjects must be willing and able to participate in all required evaluations and procedures in this study protocol including swallowing capsules without difficulty

4.1.7 Subjects must have the ability to understand the purpose and risks of the study and provide signed and dated informed consent and authorization to use protected health information

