10.0 CORRELATIVE STUDIES

10.1 Tissue Procurement

The following materials should be sent for each patient that signs consent. The slides should be done after the patient has signed the consent form to participate in the study and within 4 weeks of starting study treatment.

1. Fifteen 4 micron unstained sections on charged (plus) slides
2. Four 10 micron sections (if an incisional or excisional biopsy) or eight 10 micron sections (if needle biopsy) on slides or in a tube

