12.0 MEASUREMENT OF EFFECT

Response assessments will be evaluated based on Lugano Criteria (refer to Appendix 3). Patients who achieve a CR or PR after cycle 1 treatment will have a CT scan approximately 8 weeks after the end of study treatment. Please see section 11 for the schedule of the imaging studies. Patients will have pre-treatment and end of treatment FDG-PET and/or CT to monitor their response to treatment. For each patient, every effort will be made to use the same radiologic imaging that was obtained at screening to be used to assess response. Interim response will be assessed after cycle 1 using CT scans. During follow up patients will have CT scans done at 6, 12, and 24 months after the last cycle of therapy.

All patients will be evaluable for toxicity from the time of their first treatment with rituximab and acalabrutinib.

The following guidelines are to be used for establishing tumor measurements at baseline and for subsequent comparison:

- The six largest dominant nodes or extranodal masses must be identified at baseline.
- If there are 6 or fewer nodes and extranodal masses, all must be listed as dominant. If there are more than 6 involved nodes or extranodal masses, the 6 largest dominant nodes or extranodal masses should be selected according to the following features:
 - nodes should be clearly measurable in at least two perpendicular measurements
 - nodes should be from as disparate regions of the body as possible
- Measurements for all dominant nodes and extranodal masses will be reported at baseline. Measurements on non-dominant nodes are not required. The lymph nodes or extranodal masses selected for measurement should be measured in two perpendicular diameters, one of which is the longest perpendicular diameter. The lymph nodes should be measured in centimeters to the nearest one tenth of a centimeter (e.g. 2.0 cm, 2.1cm, 2.2 cm, etc.)

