12.1 Definitions

12.1.1 Overall Response Rate

Overall response rate (ORR) is defined as all patients that achieve a CR or PR based on end of treatment scans, using the Lugano Criteria.

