Grade	Description
0	Normal activity. Full active, able to carry on all pre-disease performance without restriction.
1	Symptoms, but ambulatory. Restricted in physically strenuous activity, but ambulatory and able to carry out work of a light or sedentary nature (e.g., light housework, office work).
2	In bed < 50% of the time. Ambulatory and capable of all self-care, but unable to carry out any work activities. Up and about more than 50% of waking hours.
3	In bed > 50% of the time. Capable of only limited self-care, confined to bed or chair more than 50% of waking hours.
4	100% bedridden. Completely disabled. Cannot carry on any self-care. Totally confined to bed or chair.
5	Dead.

APPENDIX 2

Known Strong in Vivo Inhibitors or Inducers of CYP3A

Strong Inhibitors of CYP3A^a	Strong Inducers of CYP3A^d
boceprevir	carbamazepine ^e
clarithromycin ^b	phenytoin ^e
conivaptin ^b	rifampin ^e
indinavir	St John's wort ^e
itraconazole ^b	
ketoconazole ^b	
lopinavir/ritonavir ^b (combination drug)	
mibepradil ^c	
nefazodone	
nelfinavir	
posaconazole	
ritonavir ^b	
saquinavir	
telaprevir	
telithromycin	
voriconazole	

- a. A strong inhibitor is defined as an inhibitor that increases the AUC of a substrate by \geq 5-fold.
- b. In vivo inhibitor of P-glycoprotein.
- c. Withdrawn from the United States market because of safety reasons.
- d. A strong inducer is defined as an inducer that results in \geq 80% decrease in the AUC of a substrate.
- e. In vivo inducer of P-glycoprotein.

Note: The list of drugs in these tables is not exhaustive. Any questions about drugs not on this list should be addressed to the Sponsor of the protocol.

Source:

FDA Drug Development and Drug Interactions: Table of Substrates, Inhibitors and Inducers
. Web link Accessed 11 June 2015:

<http://www.fda.gov/Drugs/DevelopmentApprovalProcess/DevelopmentResources/DrugInteractionsLabeling/ucm093664.htm#inVivo>

APPENDIX 3

Assessment of Responses based on Lugano Criteria as defined by Cheson et al³⁰

Table 3. Revised Criteria for Response Assessment		
Response and Site	PET-CT-Based Response	CT-Based Response
Complete	Complete metabolic response	Complete radiologic response (all of the following) Target nodes/nodal masses must regress to ≤ 1.5 cm in LD _i No extralymphatic sites of disease

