Lymph nodes and extralymphatic sites	Score 1, 2, or 3* with or without a residual mass on \leq PS† It is recognized in Waldeyer's ring or extranodal sites with high physiologic uptake or with activation within spleen or marrow (eg, with chemotherapy or myeloid colony-stimulating factors), uptake may be greater than normal. In these situations, if uptake is \leq liver, complete metabolic response may be inferred if uptake at sites of initial involvement is no greater than surrounding normal tissue even if the tissue has high physiologic uptake	
Nonmeasured lesion	Not applicable	Absent
Organ enlargement	Not applicable	Regressed to normal
New lesions	None	None
Bone marrow	No evidence of FDG-avid disease in marrow	Normal by morphology; if indeterminate, IHC negative
Partial	Partial metabolic response	Partial regression (all of the following) $\geq 50\%$ decrease in SPD of up to 6 target measurable nodes and extranodal sites
Lymph nodes and extralymphatic sites	Score 4 or 5† with reduced uptake compared with baseline and residual mass(es) of any size At interim, these findings suggest responding disease	When a lesion is too small to measure on CT, assign 5 mm \times 5 mm as the default value When no longer visible, 0 \times 0 mm For a node > 5 mm \times 5 mm, but smaller than normal, use actual measurement for calculation Absent/normal, regressed, but no increase Spleen must have regressed by $> 50\%$ in length beyond normal
Nonmeasured lesions	Not applicable	None
Organ enlargement	Not applicable	Not applicable
New lesions	None	
Bone marrow	Residual uptake higher than uptake in normal marrow but reduced compared with baseline (effuse uptake compatible with reactive changes from chemotherapy allowed). If there are persistent focal changes in the marrow in the context of a nodal response, consideration should be given to further evaluation with MRI or biopsy or an interim scan	
No response or stable disease	No metabolic response	Stable disease
Target nodes/nodal masses, extranodal lesions	Score 4 or 5 with no significant change in FDG uptake from baseline at interim or end of treatment	$< 50\%$ decrease from baseline in SPD of up to 6 dominant measurable nodes and extranodal sites; no criteria for progressive disease are met
Nonmeasured lesions	Not applicable	No increase consistent with progression
Organ enlargement	Not applicable	No increase consistent with progression
New lesions	None	None
Bone marrow	No change from baseline	Not applicable

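### Eligibility requires no assessable disease at baseline and the plan has no scoring rule for patients without it, so a response that predates treatment can count towards the ORR

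*Combined protocol and SAP*

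**What the plan says.** - **Entry.** Section 4.1.1: "Subjects must have a biopsy confirmed newly diagnosed CD20 positive B cell PTLD". The accepted histologies include hyperplasia-type lesions such as "Florid follicular hyperplasia PTLD". The other criteria cover age, performance status, organ function, comorbidity and concomitant drugs. None concerns measurable, assessable or FDG-avid disease. Section 11.1.1 requires screening imaging but no positive finding, and lets the investigator omit the marrow examination when suspicion is low.
- **Biopsy type.** Section 10.1 allows for removal of the lesion: "Four 10 micron sections (if an incisional or excisional biopsy".
- **Baseline measurement.** Section 12.0 calls for the six largest lesions to be identified and adds: "If there are 6 or fewer nodes and extranodal masses, all must be listed as dominant". It gives no minimum number or size.
- **Response.** Appendix 3, CT column. For CR: "Target nodes/nodal masses must regress to" 1.5 cm or less, "No extralymphatic sites of disease", no nonmeasured lesion, no new lesion, normal marrow. For PR, at least a 50% "decrease in SPD of up to 6 target measurable nodes and extranodal sites".
- **Endpoint and population.** Section 12.1.1 defines ORR as "all patients that achieve a CR or PR based on end of treatment scans, using the Lugano Criteria". Section 14.5 analyses everyone given any study treatment. The abbreviation list contains a term for nonevaluable, but no response or analysis rule uses it.
- **Decision rule.** Section 14.2 sets a null of 60%, a target of 75%, 62 patients, and success at 44 or more responses.

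**The concern.** Response should describe what happened to disease that was present when treatment began. On CT, CR is a state at the time of the scan, and a patient with nothing left to see is already in that state. PR and stable disease on CT rest on a percentage change in the summed lesion products, which is undefined when the baseline sum is zero. The plan gives no third option, so the natural reading is CR unless new disease appears.

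Such a patient adds to the numerator whatever the drugs do. That raises ORR and CRR, makes 44 of 62 easier to reach under an ineffective regimen, and makes a futility stop less likely. The interim response call also determines the number of further cycles (section 3.4), so an unassessable baseline affects more than the final count.

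**Working it through.** **Inputs.** From section 14.2: n = 62, cutoff 44, null 0.60, alternative 0.75, two-sided 10% (5% in the upper tail). From Table 5: stop at or below 5/10, 12/20, 18/30, 25/40, 32/50. Assumed: k, the number of patients with no assessable baseline disease who are scored CR.

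**Step 1: the plan's own figures.**
- P(Bin(62, 0.60) ≥ 44) = 0.0492.
- P(Bin(62, 0.75) ≥ 44) = 0.812.
- The Table 5 looks at a true ORR of 60% give an exact early-stopping probability of 0.844 (Table 6: 0.84).

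The stated design reproduces.

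**Step 2: add k CRs that do not depend on treatment, with 60% response in the rest.** Success requires k + Bin(62 − k, 0.60) ≥ 44. The expected counted ORR is [k + 0.60 × (62 − k)] / 62.

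| k | Expected counted ORR | Success probability, no looks |
|---|---|---|
| 0 | 60.0% | P(Bin(62, 0.60) ≥ 44) = 0.049 |
| 3 | 38.4/62 = 61.9% | P(Bin(59, 0.60) ≥ 41) = 0.086 |
| 6 | 39.6/62 = 63.9% | P(Bin(56, 0.60) ≥ 38) = 0.143 |

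**Step 3: apply the Table 5 looks.** The k patients are placed at random in the enrolment order (hypergeometric allocation to each cohort). Paths at or below a boundary are removed, and the remaining probability of at least 44 is summed.

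| k | Early-stopping probability | Success probability with looks |
|---|---|---|
| 0 | 0.844 | 0.040 |
| 3 | 0.778 | 0.071 |
| 6 | 0.696 | 0.119 |

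The looks lower each absolute risk but hardly change the ratios to k = 0: 0.086/0.049 = 1.8 and 0.143/0.049 = 2.9 without looks; 0.071/0.040 = 1.8 and 0.119/0.040 = 3.0 with them.

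Both tables assume that every one of the k patients stays free of progression and reaches the end-of-treatment scan. For a given k, that makes them upper values.

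**The case against.** - **Section 12.0 presumes lesions.** It says dominant lesions must be identified and measured at baseline, and Appendix 3 speaks of nodes that regress. This stands in part: CR by default is the natural scoring but is not stated as a rule. It does not close the gap. Section 12.0 is a measurement guideline with no minimum, section 4.0 sends sites to the eligibility criteria, and no rule marks these patients nonevaluable.
- **Lack of a measurable target does not guarantee CR.** A reader might infer that anyone without a measurable node can be scored only CR or progression. Appendix 3 does not support that. It has separate rows for nonmeasured lesions, organ enlargement and marrow, and it treats effusions, ascites and bone lesions as assessable. Section 11.1.2 repeats the marrow examination if it was positive at baseline. The problem is limited to patients with no assessable disease of any kind.
- **The frequency is unknown.** Section 10.1 sets section counts by biopsy type and does not say that excision clears the disease. Nothing says that the hyperplasia-type histologies lack visible lesions. This stands, and k is an assumption.
- **The null may already contain such patients.** If the series behind the 60% enrolled them too, part of the inflation is in the benchmark. The documents do not say either way.

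**Conclusion.** The gap is real. Followed as written, the plan admits patients with no assessable disease and can credit them with a response that predates treatment. It deserves correction because it bears on the primary endpoint and the 44 of 62 rule leaves little room.

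The size is a sensitivity range. Three such patients would move the false-success probability from 0.049 to 0.086 (0.040 to 0.071 with futility looks), and six would move it to 0.143 (0.119 with looks). These figures assume 60% response in the remaining patients, CR in all k, and a 60% null from series without such patients.

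A reader might infer that the trial's false-success risk is in fact nearly tripled, or that a positive biopsy alone secures entry. The documents support neither: they give no basis for six such patients, and all the other eligibility criteria still apply.

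**What to change.** **Future patients.** Add an inclusion criterion: at least one site of assessable disease remaining after the diagnostic biopsy, shown on the screening work-up. The site may be bidimensionally measurable on CT, FDG-avid on PET, or a nonmeasured or marrow site that Appendix 3 can assess. The sample size and cutoff need not change.

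**Patients already enrolled.** Keep the all-treated analysis and the 44 of 62 rule as primary. Flag patients with no assessable baseline disease, and report ORR and CRR with and without them, using the reduced denominator and its exact 90% CI. For example, if 44 of 62 included three such patients, the second analysis would be 41/59 = 69.5% (58.2% to 79.3%), against a lower limit of 60.05% for 44/62.

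These patients should not simply be struck from the count while 44 is kept. Power at 75% would fall from 0.81 to P(Bin(59, 0.75) ≥ 44) = 0.60 for three patients, or P(Bin(56, 0.75) ≥ 44) = 0.33 for six (futility looks ignored).

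**Cost.** One eligibility line, one baseline flag and one additional row in the ORR and CRR tables. Accrual falls slightly in a rare disease. Section 11.1.1 sets no order between biopsy and imaging, so a patient scanned before an excisional biopsy may need repeat imaging.
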